
[figure not shown]
Specific Aims

- Aim 1: To investigate the efficacy of active FES vs. passive FES, as measured by changes in behavioral measures. Hypothesis: We hypothesize that improvements in motor function will be significantly greater using the active FES therapy than the passive FES therapy.
- Aim 2: To investigate the relationship between brain functional activation patterns and behavior changes induced by active vs. passive FES intervention. Hypothesis: We hypothesize that changes induced by active FES (as measured by brain fMRI and EEG measures) will show greater adaptive brain reorganization changes (i.e. brain changes that correlate with improved outcomes) than that induced by the passive FES.
- Aim 3: To investigate the relationship between brain white matter integrity and behavior changes induced by active vs. passive FES intervention. Hypothesis: We hypothesize that changes induced by active FES (as measured by brain DTI measures) will show greater adaptive brain reorganization changes (i.e. brain changes that correlate with improved outcomes) than that induced by the passive FES.

Research Design and Methods

This is a prospective, longitudinal study in which stroke patients with upper-limb hemiparesis will be adaptively randomized to two groups: **Active FES (aka the experimental group)**, and **Passive FES aka (the control group)**. Adaptive randomization in our study will be done based on age and severity of UE impairment (see Figure 1).

Participants: 144 patients will be enrolled in the study following inclusion/exclusion criteria below:

Inclusion criteria: ages 50-85 years; new-onset ischemic stroke 12 months prior – chronic time frame; right hand dominant – affected arm; mild to moderate unilateral upper extremity(UE) impairment (Action Research Arm Test; ARAT score > 35) or severe unilateral upper extremity(UE) impairment (ARAT score <= 35); no upper extremity injury or conditions that limited use prior to the stroke; pre-stroke independence with a Modified Rankin Score of 0 or 1, and the ability to provide informed consent on their own behalf.

Exclusion criteria: Inability to competently participate in study procedures, Concurrent upper extremity therapy, other neurological (e.g., AD) or psychiatric disorders.

Note, participants with contraindications to MRI will continue to be eligible for this research and will be asked to participate in both the computer training and the behavioral assessments.

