For Specific Aim 2: To track fMRI and EEG-BCI based brain reorganization changes and behavioral changes induced by active vs. passive FES. Changes in fMRI and EEG derived LI values over time will be compared in the 2 groups. Group differences in LI at each time-point will be evaluated using Mann-Whitney U test. To determine if there are significant main effects for groups and time, and significant interaction of Group X Time, we will perform Linear Mixed Model analyses. To test if change in fMRI and EEG derived LI, across multiple time-points correlate with change in behavioral measures: The difference in each measure, example from time-point 1(T1) to T2 (i.e. change score, Δ LI) will be calculated and separate correlation (Pearson or Spearman rho) analyses will be performed to see if change in fMRI and EEG significantly correlate with change in behavioral scores (Δ ARAT or Δ SIS-hand function etc).

EEG Data Statistical Analysis: The independent variables are the signed r-squared values and the coherence estimates. At individual participant level the data consists of average estimates per session for condition/movement/screening phase combination sets, and at group level the estimates consist of grand averages over sessions of each individual participant data in the group. Nonparametric statistical tests will be run by calculating Monte-Carlo estimates of the significance probabilities and critical values from the permutation distribution (Oostenveld et al., 2007), followed by correction for multiple comparison using false discovery rate (FDR). Our priori hypotheses regarding expected changes in the r-squared values and coherence as a result of intervention at C3 and C4 sites will be tested using paired t-tests in MATLAB.

For Specific Aim 3: To track DTI based brain reorganization changes and behavioral changes induced by active vs. passive FES. The Pearson r or non-parametric Spearman rank correlation test, as appropriate, will

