be used for correlation analyses between DTI and motor outcome measurements. To test whether change in FA and other diffusion values across multiple time-points correlate with change in scores on the ARAT and the SIS: The difference in each measure, example from time-point 1(T1) to T2 (i.e. change score, Δ FA or other diffusion metrics) will be calculated and separate linear regression analyses performed to see if change in diffusion values significantly correlate with change in behavioral scores. Volume of lesion affecting the white matter will be entered as covariate in the regression analysis.

Sample size considerations: Our sample size analysis is based on the primary outcome measure ARAT. For observing a minimally clinically significant difference on the ARAT of 6 points with a standard deviation of 12, from pre to post intervention, we would need a sample size of 44 participants per cell (Age By Severity with 2 levels each). This would give us 90% power to detect a significant difference. This leads to an estimated sample size of $44 \times 4 = 176$. With 10% additional recruitment to account for data loss due to participant drop-out or poor quality, we propose to recruit a total of $N = 192$ participants in this study.

Given the challenges in recruiting this population (based on our ongoing study – approved under 2010-0004, 2015-0469), we propose to also recruit patients who have contraindications for MRI and allow these patients to complete the behavioral assessments and intervention components of the study.

With the aim of meeting our sample size requirements, and also to recruit a diverse population, we had teamed up with collaborators at Milwaukee, who are also involved in stroke rehab work. Unfortunately, the original PI at Milwaukee has since moved; we have therefore decided to try and meet our goal of 144 at UW Madison and increase our efforts to recruit from the neighboring counties.

Potential Risks and Benefits

EEG Recording: The EEG electrodes are passive and only record ongoing physiological activity. Risks related to the EEG recording system include skin irritation, an unpleasant electrode gel smell, and mild discomfort associated with applying, wearing, and removing electrodes on the scalp, face, chest, and hand.

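### Aim 3 hypothesises greater adaptive DTI change under active than passive FES, but its planned analyses compare no diffusion measure between arms and include no Group term

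*Combined protocol and SAP*

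**What the plan says.** Under Specific Aims, Aim 3 is to study how white matter integrity relates to behaviour change under the two interventions. Its hypothesis is directional and between arms: "changes induced by active FES (as measured by brain DTI measures) will show greater adaptive brain reorganization changes" than passive FES. Adaptive changes are defined there as those that correlate with better outcomes.

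Under Data Processing/Data Analysis, the Aim 3 paragraph opens with the arm contrast: "To track DTI based brain reorganization changes and behavioral changes induced by active vs. passive FES". It then lists two analyses:

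- Pearson or Spearman coefficients, to "be used for correlation analyses between DTI and motor outcome measurements".
- Change-score analyses, introduced by "To test whether change in FA and other diffusion values across multiple time-points correlate with change in scores on the ARAT and the SIS" and carried out as "separate linear regression analyses performed to see if change in diffusion values significantly correlate with change in behavioral scores". The one adjustment named is "Volume of lesion affecting the white matter will be entered as covariate in the regression analysis".

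The Aim 2 paragraph does name an arm comparison for its own measures: "Changes in fMRI and EEG derived LI values over time will be compared in the 2 groups". It adds a Mann-Whitney test at each time-point and, for the "significant interaction of Group X Time, we will perform Linear Mixed Model analyses". Aim 1 likewise puts Group in a mixed model, for the behavioural measures.

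**The concern.** A hypothesis that one arm shows more of something needs an estimate of the difference between arms. Aim 3 plans none. Its heading names both interventions, but the analyses beneath it ask only whether diffusion change and behaviour change go together.

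The risk is in the reporting. A significant diffusion-behaviour association, set under a heading that names active versus passive FES, could be presented as support for active FES when it carries no information on which arm it came from. The text also does not say whether the regressions pool the arms or are run in each arm. If they are run per arm, a reader may be tempted to contrast a significant result in one arm with a non-significant result in the other, which is not a test of the difference.

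**Working it through.** **1. Which paragraph tests what**

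| Analysis paragraph | Outcome | Between-arm test |
|---|---|---|
| Aim 1 | Behavioural measures (ARAT, SIS) | Mixed model with Group and Time |
| Aim 2 | fMRI and EEG laterality index (LI) | Mann-Whitney; Group X Time mixed model |
| Aim 2, change scores | LI with behaviour | None |
| Aim 3, correlations | DTI with motor outcomes | None |
| Aim 3, change scores | Diffusion with behaviour, lesion volume adjusted | None |

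The count of planned between-arm DTI tests is zero. This step needs no assumption. The plan gives no power figure for Aim 3 to reproduce; Sample size considerations deals with the ARAT only.

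**2. Assumptions for the illustration (not in the documents)**

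The allocation is 72 per arm. MRI is optional, so the number scanned is unknown. I take 65 (72 x 0.9 = 64.8, using the plan's 10% loss figure), 50 and 36 (half of 72) per arm. Tests are two-sided at 0.05. Behaviour change = r x brain change + noise.

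**3. Pooled regression with lesion volume and no Group, 65 per arm (simulated)**

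Common slope in both arms; the arms differ in mean brain change by 0 or 0.6 SD:

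| r in both arms | Pooled regression significant, 0 vs 0.6 SD | Between-arm test of brain change, 0 vs 0.6 SD |
|---|---|---|
| 0.1 | 20% vs 21% | 5% vs 92% |
| 0.2 | 63% vs 67% | 5% vs 92-93% |
| 0.3 | 94% vs 96% | 5% vs 92% |

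Repeat runs at r = 0.2 put the pooled result at 0.6 SD between 65% and 67%.

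Different slopes, no difference in mean brain change:

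| r active / r passive | Pooled regression significant |
|---|---|
| 0 / 0 | about 5% |
| 0.2 / 0.2 | about 63% |
| 0.4 / 0 | about 63% |
| +0.4 / -0.4 | 6% (brain change x Group interaction: 99.8%) |

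The second and third rows cannot be told apart by the planned test. One has identical arms; the other has all the association in the active arm.

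**4. If the regressions are run per arm**

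Let p be the power in one arm: approximately P(Z > 1.96 - atanh(r) x sqrt(n - 3)), plus a negligible opposite tail. With the same true r in both arms, significance in the active arm only has probability p(1 - p).

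- n = 65: r = 0.2, 0.358 x 0.642 = 0.230; r = 0.3, 0.683 x 0.317 = 0.216.
- n = 50: 0.285 x 0.715 = 0.204; 0.564 x 0.436 = 0.246.
- n = 36: 0.214 x 0.786 = 0.168; 0.428 x 0.572 = 0.245.

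So about 17-25% of trials would show that pattern with no true difference. The rate depends on r: at r = 0.5 it is 1% at 65 and 3% at 50 per arm.

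**5. What between-arm tests could detect at 80% power**

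Mean difference from the two-sample t-test; Fisher-z difference = 2.80 x sqrt(2/(n - 3)).

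| n per arm | Mean difference | Fisher-z difference | Example |
|---|---|---|---|
| 65 | 0.50 SD | 2.80 x sqrt(2/62) = 0.50 | r = 0.10 vs 0.54 |
| 50 | 0.57 SD | 2.80 x sqrt(2/47) = 0.58 | r = 0.10 vs 0.59 |
| 36 | 0.67 SD | 2.80 x sqrt(2/33) = 0.69 | r = 0.10 vs 0.66 |

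**The case against.** Four replies deserve an answer.

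- *The aim is about a relationship, and the planned analyses address it.* This stands in part. Aim 3 does set out to study how white matter and behaviour change are related, and the correlations and regressions serve that. What they leave out is the comparison stated in the hypothesis.
- *The Group X Time mixed model may be meant to cover DTI.* That sentence names no outcome, but it sits in the Aim 2 paragraph straight after the LI comparisons, and that paragraph does not mention DTI. If DTI is intended, the plan should say so.
- *The regressions may be fitted separately by arm.* The text does not say this. The word separate follows a sentence about differencing each measure, which suggests one fit per measure. Fits by arm would still need a test of their difference.
- *The pooled regression does respond to some arm differences.* This stands. A reader might infer from the common-slope results that the pooled test looks the same whether or not the arms differ. That holds only when the slope is common. With r = 0.4 active and 0 passive, significance rises to about 63%, against about 5% with no association in either arm. The limit is attribution: a common r = 0.2 gives the same 63%.

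**Conclusion.** The point holds. Followed as written, the plan leaves Aim 3's comparative hypothesis without a test, and this conclusion rests on the text alone. The percentages are illustrations that depend on the assumed correlations, arm differences and numbers scanned.

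Stronger readings are not supported. A reader might infer that the plan ignores treatment arm in its imaging work generally; Aim 2 compares LI between arms, and its lesser gap is only that the LI-behaviour association is not compared. A reader might also infer that the efficacy conclusion is at risk; Aim 1 has Group in its model and ARAT is the primary outcome, so it is unaffected. Aim 3 is a mechanistic aim, and the correction should be made before its data are analysed.

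**What to change.** 1. Apply to the DTI metrics the Group X Time linear mixed model already planned for LI. Make FA, the one diffusion metric the plan names, the principal metric. Make the Group difference in change from baseline to post-intervention, with 95% CI, the main contrast. Treat the mid and 1-month time-points and other metrics as supportive.
2. In the Aim 3 change-score regressions, keep lesion volume and add Group and brain change x Group. Report the interaction with 95% CI alongside item 1, not in place of it: with a common slope the interaction is null even when active FES produces more brain change. Do the same, secondarily, for the Aim 2 brain-behaviour analyses.
3. State that no pooled or single-arm association will be reported as evidence of a difference between active and passive FES.

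Two further steps are optional and would be changes to the plan. One is measuring DTI change from the average of the two baselines: the averaging is described under Aim 1, while the Aim 3 example is T1 to T2. The other is extending the false discovery rate correction, planned only for EEG, to the supportive DTI metrics; this would lower power for them.

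The cost is wording only, on data the trial already collects. The plan should state the downside: the number scanned is unknown, and only fairly large arm differences would be detectable, about 0.50 to 0.67 SD in mean change or 0.50 to 0.69 in Fisher z over the assumed 65 to 36 per arm.

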Randomization: Patients will be adaptively randomized, based on age (50-64 years and 65-85 years), and severity (severe – ARAT > 35, non-severe – ARAT <= 35), to two groups – the active FES group receiving intervention with the active FES (n = 72) and the passive FES group receiving FES only intervention (n=72). Advancing age has a major negative impact on stroke morbidity, mortality; older adults (> 65 years) have increased chance of dying after stroke and being discharged to the skilled nursing facility if they survive, therefore age 65 will be used as a cut-off. There is some evidence that patients with ARAT scores above or below 35 show clear differences in recovery [41], therefore ARAT of 35 will be used as a cutoff.

Subject identification and Recruitment

Subject Identification:

- a) Through referrals by the Stroke Neurology team or other UWHC or UW Rehab hospital or The American Center (TAC) clinicians involved in patient care, in the in-patient or outpatient setting.
- b) Clinicians involved in the care of patients may send recruitment letters to eligible patients and ascertain their interest in study participation.
- c) A stroke service patient log maintained by the UW-Madison Stroke Neurology section UWHC or UW Rehab hospital or TAC clinicians will be used to identify patients.
- d) By posting recruitment flyers in community newsletter, at different locations such as the UWHC, the School of Medicine, UW libraries, the University Station Clinic, St. Mary's hospital, Meriter hospital, as well as UW out-patient clinics and rehab centers outside the Madison area, Madison public libraries, stroke support and other aging support group locations, and on the Principal Investigator, [name] lab

webpage <http://radiology.wisc.edu/research/>. We will also release ads regarding recruitment in the media – in major newspapers such as the Wisconsin State Journal, the Milwaukee Sentinel, in the Isthmus, and through the Wisconsin Public Radio (WPR).

e) [name], the radiologist involved in clinical imaging protocols of patients, will identify patients who are suitable for study participation as they present to the UWHC, UWMF, WIMR, or Health Emotions Research Institute (HERI) for clinical imaging.

f) We have permission to contact participants who have participated in other stroke research conducted by our group ([name] 2013-1561, 2015-0469 and 2018-0398). We propose to contact these patients and ascertain interest in participating in this study.

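### The only stated power (90%) belongs to 176 evaluable patients and a pre-to-post change; none is given for the planned 144 or for active versus passive FES

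*Combined protocol and SAP*

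**What the plan says.** Two sample sizes stand in the current text of the combined protocol and SAP.

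- **Data Processing/Data Analysis, Sample size considerations.** ARAT is named as the primary outcome. The target is set as: "For observing a minimally clinically significant difference on the ARAT of 6 points with a standard deviation of 12, from pre to post intervention". The section continues: "we would need a sample size of 44 participants per cell (Age By Severity with 2 levels each). This would give us 90% power". It multiplies 44 by 4 to reach 176, then adds an allowance: "With 10% additional recruitment to account for data loss due to participant drop-out or poor quality", ending with "we propose to recruit a total of $N = 192$ participants in this study".
- **Same section, two paragraphs later.** After reporting that the lead of a collaborating site had moved, it says: "we have therefore decided to try and meet our goal of 144 at UW Madison".
- **Research Design and Methods, Participants.** "144 patients will be enrolled in the study following inclusion/exclusion criteria below".
- **Randomization.** "Patients will be adaptively randomized, based on age (50-64 years and 65-85 years" and by ARAT severity, with 72 patients in each arm.

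The comparison of interest is stated in Specific Aims, Aim 1: "improvements in motor function will be significantly greater using the active FES therapy than the passive FES therapy". The Aim 1 analysis (item 1a) is a linear mixed model with Group (active, passive) and Time (four levels). Age and severity are not named as terms in it.

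**The concern.** The 90% is tied to a size that the rest of the protocol does not plan: 144 is 75% of 192 (144/192) and falls short of 176 even with no loss. It is also tied to a different question. The sizing describes a change from before to after the intervention in age-by-severity cells and does not mention treatment arm, while Aim 1 is a between-arm comparison.

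A reader therefore cannot tell what chance the trial has of detecting a difference between active and passive FES. A null result could be read as coming from a trial with 90% power for that comparison, which the document never shows. The per-cell wording also invites the belief that each age-by-severity cell is powered in its own right, although those factors serve only to guide randomization.

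**Working it through.** **Inputs from the document:** 6 points; SD 12; 44 per cell; four cells; 90% power; 10% added for loss; 144 planned, 72 per arm.

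**Assumed, because not stated:** two-sided alpha 0.05; SD 12 is the SD of the pre-to-post change; t-tests; for the arm comparison, 6 points is the between-arm difference in change; 10% of the 144 are lost. Standardised effect d = 6/12 = 0.5. Power is from the noncentral t distribution.

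**1. Reproduce the plan's figure.** One-sample t-test on change, noncentrality d√n, n − 1 df. The n for 90% power is 43.995, so 44. At n = 44 the noncentrality is 0.5 × √44 = 3.317 and power is 90.0%. This matches. A two-sample test with the same inputs needs 86 per arm (n = 85.03), so 44 is not a per-arm number. That the one-sample test was the one used is an inference.

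**2. Totals.** 44 × 4 = 176, correct. 176 × 1.10 = 193.6 and 176/0.9 = 195.6; the stated 192 is slightly below both, which is immaterial.

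**3. Same test at 144.** If the four cells are equal, 144/4 = 36 per cell and 36 × 0.9 = 32.4 after loss.

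- 36 per cell: noncentrality 3.000, power 83.1%
- 32.4 per cell: noncentrality 2.846, power 78.8%

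Equal cells are an assumption; the Randomization section sets no quotas for them.

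**4. Arm comparison.** Two-sample t-test on change, noncentrality d√(n/2), 2n − 2 df. With 10% loss, 144 × 0.9 = 129.6, about 65 per arm. If 144 instead already contains the 10% addition, 144/1.1 = 130.9, again about 65 per arm.

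- 88 per arm (176): power 91.0%
- 72 per arm (144, no loss): power 84.6%
- 65 per arm (144, 10% loss): power 80.8%
- Difference detectable with 90% power: 6.5 points (72 per arm), 6.9 points (65 per arm)

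**5. Sensitivity of step 4 at 72 / 65 per arm.**

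- 5-point difference: 70.0% / 65.5%
- 4-point difference: 51.1% / 47.1%
- One-sided 0.05, 6 points: 91.0% / 88.3%
- SD 12 is cross-sectional, so SD of change = 12√(2(1 − ρ)): 78% / 73% at pre-post correlation ρ = 0.4; 97% / 95% at ρ = 0.7; 90% is reached at ρ of about 0.58 / 0.62

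**6. Active versus passive inside one cell, equal cells.** 22 v 22 (176 in total) gives 37%; 18 v 18 (144 in total) gives 31%. The 90% cannot be read as within-cell power for the treatment effect under these inputs.

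**The case against.** **The 176/192 text may simply be left over.** The paragraph on the collaborating site explains why recruitment is now confined to one centre, and 176/192 may survive from a larger plan. That is plausible, and it makes this mainly a paragraph that was not updated. But the paragraph does not withdraw 192, and it gives no power for 144.

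**The benchmark rests on assumptions that are not the sponsor's.** This stands. Step 5 runs from 47% to 97%, and some readings reach 90% at 144. One-sided 0.05 in the one-sample test even needs exactly 36 per cell (n = 35.65; 36 × 4 = 144), although it does not give the document's 44. The inconsistency and the missing power statement do not depend on any of these choices.

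**The mixed model is not a t-test.** This stands too, in both directions. Repeated measures and an averaged baseline may add precision. But item 1a does not name the contrast to be tested. An overall 3-df Group by Time test, if the other visits added nothing to the pre-post contrast, would have roughly 71% power at 72 per arm and 66% at 65 per arm (chi-square approximation, noncentrality 72/2 × 0.25 = 9.0 and 65/2 × 0.25 = 8.1).

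**Stronger readings a reader might infer.** One is that the chance of missing an active-versus-passive difference has risen from 10% to 15–19%. The document never claims 90% power for that comparison, so there is no 10% to measure against. Another is a single power range of 79–85% for Aim 1. That would join the low end of the within-cell pre-post test to the high end of the two-arm test; the arm comparison on the stated assumptions is 81–85%.

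**Conclusion.** The point holds as an internal inconsistency with a missing justification. The stated power does not belong to the planned size, and it is not shown to apply to the Aim 1 comparison. This needs no assumption: it follows from setting the sample size section beside the design, randomization and aims text. It is not an arithmetic error, since 44 reproduces and 44 × 4 is 176.

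Its numerical size is illustrative only. The calculation that reproduces 44 falls from 90% to about 83% at 144, or 79% after 10% loss, given equal cells. The arm comparison has about 85%, or 81% after loss, given a two-sample t-test on change, two-sided 0.05, SD of change 12 and a 6-point between-arm difference. The documents do not support a conclusion that the trial is underpowered for Aim 1; they support only that its power is not stated. This should be fixed.

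**What to change.** Use one total, 144 (72 per arm), throughout, and say whether it is before or after loss. Remove 176, 192 and the 90% claim as the operative basis, and do not claim 90% power within age-by-severity cells.

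Restate power, or the difference detectable with a chosen power, for active versus passive FES at 144. The sponsor should state and justify:

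- alpha and sidedness
- the SD of pre-to-post ARAT change
- the between-arm difference targeted (the present 6 points is described as a pre-to-post change)
- the loss allowance
- the contrast tested in the mixed model

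The 81–85% above shows the form such a statement would take; it should not be adopted without a source for each input.

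The cost is protocol wording and a recalculation. No extra enrolment is required. The downside is that the stated power will probably be less favourable than 90%, and the sponsor must commit to assumptions now left open.
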